## **6. Secondary analyses.**

### **a. Multivariable-adjusted outcome logistic regression analysis**

Within the larger Data Partners sites, we will apply an outcome logistic regression analysis adjusting for the same confounders and compare the results with those from the propensity score approach. If the results from propensity score analysis and regression analysis at large Data Partner sites differ, we will reassess our data and propensity score model to ensure accuracy of the data and model. If necessary, we will perform a sensitivity analysis for unmeasured confounding by calculating the Rosenbaum bounds for propensity score matched data.

### **b. Moderate and severe hypersensitivity reactions**

Moderate and severe hypersensitivity reactions, adjudicated using methods in Brown's study, will be combined as a single outcome variable in a secondary analysis. We will then analyze the risk of a moderate or severe hypersensitivity reaction among iron dextran users compared to other parenteral iron users, as described above.

## 7. Sample size calculation

From the feasibility assessment results, we estimated that there were 40,015 new iron dextran users and 60,714 new users of other iron products who did not have a diagnostic code for dialysis in the previous 183 days. We varied the baseline risks of analysis and epinephrine administration according to the modular program results, and computed the least detectable relative risk at a 0.05 significance level with a power of approximately 80% using the Fischer Exact Test. In our power calculation, we used the relative risk instead of odds ratio because the outcome variable is rare. Given the incidence of this rare outcome, the results of these approaches are identical to at least 2 decimal places (Table 7).

The workgroup determined, with the input of the FDA, that a study with enough power to detect a relative risk of four was adequate to perform a protocol-based assessment. FDA opinion determined that, given the rarity of the outcome (anaphylaxis), a relative risk of four or higher would be great enough to influence policy decisions. Because our least detectable relative risks are all smaller than four, the study has sufficient sample size for the primary objective.

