Iribarren et al. evaluated the validity of ICD-9-CM code 995.0 among a cohort of patients diagnosed with asthma and a comparison group of patients without asthma enrolled in Kaiser Permanente Northern California (also a Mini-Sentinel Data Partner) between 1996 and 2006. Administrative and claims data from hospitalizations, emergency department visits, and ambulatory encounters were assessed. Medical record review was conducted and cases were confirmed based upon the *Summary Report of the Second National Institute of Allergy and Infectious Disease/Food Allergy and Anaphylaxis Network symposium*. Of the 109 potential cases reviewed, 57 (52%) were confirmed as likely or probable cases.

The Mini-Sentinel Anaphylaxis Validation Workgroup developed and validated an algorithm consisting of diagnostic, symptom, and treatment codes in the Mini-Sentinel Distributed Database (MSDD). In a review of 122 patients for whom complete charts were received, 77 were judged by physician adjudicators to have anaphylaxis. The PPV for the algorithm was 63.1% (95% confidence interval [CI]: 53.9%-71.7%). The PPV was highest among inpatient visits with the ICD-9-CM codes 995.0 or 999.4. The workgroup report recommended chart review validation when using the algorithm in future medical product safety assessments, due to the low PPV.

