#### D. CHART REVIEW VALIDATION OF CASES OF POTENTIAL ANAPHYLAXIS

The chart review will follow an approach modified from the previous Mini-Sentinel validation studies, including: (1) identification of a clinical definition for anaphylaxis for use with medical records data; (2) identification, retrieval, and de-identification of medical records of patients who have been identified by Data Partners utilizing the algorithm for anaphylaxis (Table 2); (3) chart abstraction by a trained abstractor using a structured abstraction form; and (4) adjudication of anaphylaxis cases based on physician review of the completed data abstraction forms.

We will obtain all relevant portions of the medical record. The record will be redacted, abstracted, and reviewed. Because the number of anaphylaxis cases will likely be small, the goal is to validate all potential cases. Two physicians will review abstracted information and, if they feel it necessary, redacted charts and make judgments about whether anaphylaxis occurred. They will use the clinical definition developed by a recent consensus group and published by Sampson *et al.* as the gold standard for determining whether anaphylaxis occurred. Only events classified as cases of anaphylaxis, determined based on the clinician definition developed by Sampson *et al.* will be in the primary analysis (Table 2).

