## 5. Analysis comparing risk of anaphylaxis between parenteral iron dextran and other iron products

### a. Estimation of relative risk

We will employ two propensity score-based approaches – matching and stratification – to investigate the association between the use of iron dextran and anaphylaxis, with use of other parenteral iron products as the comparison group. We will assess the covariate balance after matching and stratification. The propensity score is defined as the probability of receiving iron dextran given the measured confounders. We use the propensity score methods as our primary approach because the number of anaphylaxis events is expected to be small and the number of confounders is relatively large. The propensity score approach overcomes this issue by allowing us to adjust for all measured confounders simultaneously through a composite summary score. We will estimate the propensity scores by site using a logistic model common to all Data Partners using the probability of receiving iron dextran as the dependent variable and covariates in Table 5 as independent variables.

Propensity score matching will be conducted within sites. We will match one iron dextran user with one other iron product user using 1:1 nearest-neighbor matching without replacement

with a caliper of 0.05. Unmatched patients will be excluded from subsequent analyses. Each Data Partner will transfer an aggregated dataset of the matched cohort, which includes only the number of users and outcome events in each treatment group, to the project team. The project team will then estimate the odds ratio of the confirmed anaphylactoid/anaphylaxis event, from the Sampson criteria, comparing iron dextran users with other iron product users. The aggregated dataset will only include the number of users and outcome events within each treatment group. By matching one iron dextran user with one other iron product user with similar propensity score, we estimate the average treatment effect among the treated (ATT). Thus, we will also do propensity score stratification to estimate the population-wide average treatment effect (ATE).

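### Table 7 overstates power and understates the detectable relative risks, because it ignores 1:1 matching and chart confirmation; the relative-risk-of-4 criterion is then only marginally met in the matched analysis

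*Protocol*

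**What the plan says.** Protocol section II.G.7 takes its group sizes from the feasibility assessment: "we estimated that there were 40,015 new iron dextran users and 60,714 new users of other iron products". On the risks it says: "We varied the baseline risks of analysis and epinephrine administration according to the modular program results" (the first item presumably means anaphylaxis). From these it "computed the least detectable relative risk at a 0.05 significance level with a power of approximately 80% using the Fischer Exact Test". Table 7 lists 12 rows, with baseline risks of 2.05-2.65 and 7.50-9.50 per 10,000, RRs of 2.80 down to 1.70, and power of 78.9-81.5%. The rows are not labelled by outcome. An RR of 4 was set, with FDA input, as the adequacy threshold, and the section concludes: "Because our least detectable relative risks are all smaller than four, the study has sufficient sample size for the primary objective".

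The analyses are described elsewhere:

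- Section II.G.5.a names two propensity score approaches, matching and stratification, and treats the propensity score methods together as primary. Matching is 1:1 within site with a caliper of 0.05, and "Unmatched patients will be excluded from subsequent analyses". Stratification keeps each site's whole population.
- Section II.D limits the primary outcome: "Only events classified as cases of anaphylaxis" on the clinical definition enter the primary analysis.
- Section I.C reports on the claims algorithm: "The PPV for the algorithm was 63.1"%, with a 95% confidence interval of 53.9-71.7%. It records that chart review was recommended because this value is low.

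**The concern.** The power table and the planned analyses differ in two ways, and both push power down.

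1. **Patients.** The matched analysis can hold at most 40,015 users per group. At least 60,714 - 40,015 = 20,699 comparators (34%) must drop out, and more pairs are lost wherever a dextran user finds no match within the caliper.
2. **Events.** The risks appear to be code-based feasibility risks, while only adjudicated events count. Epinephrine administration, which the section says was also used for the risks, triggers chart review; it is not the outcome.

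The adequacy of the assessment rests on this table. With detectable RRs of 1.70-2.80 the study seems to have a wide margin below 4. If the true figures lie between 3 and 4 at the lower risks, the margin is thin, and a null matched result would carry less information than the table suggests.

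**Working it through.** **Inputs.** Group sizes, baseline risks p0, RRs, alpha 0.05 and the Fisher test come from section II.G.7 and Table 7. PPV 63.1% (53.9-71.7%) comes from section I.C. The section does not give sidedness; two-sided is assumed.

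**Formula.** Power = sum over (x, y) of Bin(x; n1, RR × p0) × Bin(y; n0, p0) × 1[two-sided Fisher p ≤ 0.05]. The chart-confirmation step replaces p0 by p0 × PPV, with the same PPV in both groups.

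**Step 1: reproduce Table 7.** Row 1 has n1 = 40,015, n0 = 60,714, p0 = 2.05 per 10,000, RR 2.80 and stated power 81.3%. Exact enumeration gives 84.0%, and 80.0-84.0% over the 12 rows. The Walters arcsine approximation to Fisher's test gives 80.7%, and lies within 0.7 points of the table in every row. Exact enumeration with the two sizes exchanged gives 81.7%, within 0.4 points in every row. With 40,015 per group the exact result is 70.9%, which does not reproduce the table. Table 7 therefore used the full, unmatched cohort.

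**Step 2: expected events in row 1.**

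- Dextran: 40,015 × 0.000205 × 2.80 = 23.0. Comparator: 60,714 × 0.000205 = 12.4 in the full cohort, or 40,015 × 0.000205 = 8.2 matched.
- After × 0.631: dextran 14.5; comparator 7.9 full or 5.2 matched. The baseline becomes 2.05 × 0.631 = 1.29 per 10,000.

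**Step 3: exact power at Table 7's own RRs.**

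| Setting | Row 1 | All 12 rows |
|---|---|---|
| Stated in Table 7 | 81.3% | 78.9-81.5% |
| 40,015 pairs, no PPV | 70.9% | 69-72% |
| 40,015 pairs, PPV 63.1% | 48.3% | 46-51% |
| 40,015 pairs, PPV 53.9% | 41.2% | 40-44% |
| Full cohort, PPV 63.1% | 63.8% | 60-64% |

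The full-cohort line approximates the stratified analysis; it ignores the strata and any site exclusions.

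**Step 4: the RR-of-4 criterion at the lowest baseline, 2.05 per 10,000.**

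| Setting | Detectable RR (80% power) | Power at RR 4 |
|---|---|---|
| Full cohort, PPV 63.1% | 3.28 | 93.5% |
| Full cohort, PPV 53.9% | 3.54 | 89.1% |
| 40,015 pairs, no PPV | 3.04 | 97.2% |
| 40,015 pairs, PPV 63.1% | about 3.8 | 84.7% |
| 40,015 pairs, PPV 53.9% | 4.10 | 77.9% |
| 80% of dextran users matched (assumed), PPV 63.1% | 4.24 | 74.8% |
| 60% matched (assumed), PPV 63.1% | 4.97 | 59.6% |

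At 2.65 per 10,000 with 40,015 pairs, the detectable RR is 3.35 at PPV 63.1% and 3.61 at PPV 53.9%, so the criterion is met there.

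**Step 5: cases found through epinephrine.** If 2-10% of epinephrine-only flags are confirmed (assumed), and those flags number about 7.50 - 2.05 = 5.45 per 10,000, the baseline becomes 1.29 + 0.02 × 5.45 = 1.40 to 1.29 + 0.10 × 5.45 = 1.84 per 10,000. Over 80-100% matching, power is then 79-95% at RR 4 and 42-65% at RR 2.8.

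If the 7.50 and 9.50 rows are scaled directly instead, with 40,015 pairs, the detectable RRs are 2.91 and 2.63 at an assumed 30% confirmation, and 5.07 and 4.44 at an assumed 10%.

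**The case against.** The strongest reply is that the section claims only that the detectable RRs lie below 4, and the recalculation does not overturn this. That is correct. With perfect matching and PPV 63.1% every row stays below 4, and the full cohort stays below 4 even at the lower PPV limit. A reader might infer that the study is underpowered for its stated criterion; the documents do not support that. Breaching 4 takes the lower PPV limit in the lowest rows of the matched analysis, or a match fraction that the protocol does not give.

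Second, matching is not the sole primary analysis. Stratification keeps the entire population, so Table 7's group sizes suit it and only the confirmation factor applies. This also stands, but that factor alone brings power at the table's RRs down to 60-64%.

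Third, the 63.1% comes from a separate validation study and may not carry over to patients just given parenteral iron, and confirmed epinephrine-only cases would add events. So 48.3% in row 1 is low if such cases occur. Step 5 shows that a modest allowance restores much of the power at RR 4 but not at RR 2.8.

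A reader might also infer that dropping zero-event sites costs further power. Those sites hold users but no events, and add nothing to a site-stratified ratio. No loss can be quantified from the document. Nor does the protocol claim that a null result would exclude RRs of 2.5-3; section I.F disclaims definitive evidence.

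**Conclusion.** The point holds as an error in the stated power table, not as proof that the sample is insufficient. Table 7 matches neither planned analysis: it lacks the matching loss for one and the confirmation factor for both. Against the stated 78.9-81.5%, power at the table's own RRs is 69-72% from perfect matching alone, which needs no outside figure. It is about 46-51% matched and 60-64% in the full cohort once the protocol's own PPV is applied.

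The RR-of-4 claim is supported for the stratified analysis. For the matched analysis it is marginal at the lowest baseline risk.

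The assumptions are a two-sided test, risks that precede chart review (inferred from their being modular-program results), the unlabelled 2.05-2.65 rows being algorithm hits, equal PPV in both groups, and, outside step 5, no confirmed cases from epinephrine-only flags. The match fractions below 100% and the epinephrine confirmation rates are assumed.

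**What to change.** In section II.G.7:

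- Replace Table 7 by two panels, one for the matched analysis over a stated range of match fractions (for example 100%, 80% and 60% of 40,015) and one for the stratified full cohort.
- Scale the baseline risks by the PPV range of 53.9-71.7%, and say whether the feasibility risks precede chart review.
- Label each row by outcome source, and rescale the rows based on epinephrine administration by a stated, assumed confirmation rate.
- State the sidedness of the test.
- Restate the sufficiency sentence with the resulting range of detectable RRs, saying that the RR-of-4 claim is supported by the stratified analysis and only marginally by the matched one.

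The cost is one table and a few sentences. The stated detectable RRs become less favourable. No new data, patients or analyses are needed.

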**Table 7. Sample size power calculations**

Baseline risk per 10000 patients	Relative Risk	Power
2.05	2.80	81.3%
2.15	2.70	79.6%
2.25	2.70	81.5%
2.35	2.60	79.3%
2.45	2.60	81.1%
2.55	2.55	80.7%
2.65	2.50	80.2%
7.50	1.80	80.8%
8.00	1.75	78.9%
8.50	1.75	81.4%
9.00	1.70	78.9%

Baseline risk per 10000 patients	Relative Risk	Power
9.50	1.70	81.1%

## H. POTENTIAL LIMITATIONS AND ATTEMPTS TO MINIMIZE THEM

### 1. Misclassification bias

Bias could be introduced by the misclassification of the exposure, parenteral iron, or the outcome, anaphylaxis. We will review all cases meeting criteria for anaphylaxis or identified with an administration of epinephrine to minimize misclassification while at the same time using a sensitive measure for more complete capture of cases. We will have two adjudicators independently review all potential cases of anaphylaxis to reduce misclassification of the outcome. This will reduce potential false positives but will not address false negatives. Adjudicators will be blinded to the specific parenteral iron product used. For the exposure of interest, iron dextran, we expect there will be some unavoidable grouping of high molecular weight and low molecular weight forms. However, since the literature indicates that these forms are often confused and substituted in clinical practice, it seems necessary to combine them in our study. As a result, we will not be able to estimate the risk of anaphylaxis separately for high and low molecular weight iron dextran. We will review each chart where the patient developed anaphylaxis in an attempt to ascertain whether the iron dextran agent involved was INFeD or Dexferrum. In addition, for all cases of anaphylaxis we will collect information about whether the patient received premedication (e.g., diphenhydramine, IV fluids, or corticosteroids) and, if so, which medications were used.

### 2. Confounding

Confounding could be introduced if iron dextran and other iron products are prescribed for different reasons that are also predictive of the outcome of interest. It is possible that some providers may avoid iron dextran in patients they believe to be at high risk for anaphylaxis or in general, due to the perceived risk of anaphylaxis. We have identified a list of potential confounders that will be adjusted for in the analysis. The fact that anaphylaxis is a rare outcome does make traditional adjustment for confounding, such as multivariable-adjusted outcome regression analysis, difficult. Thus, we will also employ propensity score analysis to adjust for confounding.

There was an interest in performing a stratified analysis of the association between parenteral iron use and anaphylaxis by indication. However, because the feasibility analysis indicates that the number of patients with anaphylaxis will be low, we anticipate that it is unlikely we will have adequate power to perform these stratified analyses. In this case, indication will be used to describe the population of study.

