### 4. Indications of use

We will identify one or more indications for the use of parenteral iron for each patient (Table 6), using ICD-9-CM codes in the MSDD diagnosis file during 183 days prior to (and including) the index date. We will allow patients to have more than one potential indication. For those patients receiving parenteral iron who do not have any of these diagnostic codes, we will categorize as “other indication”. For patients categorized as “other indication”, we will obtain a list of all diagnostic codes within 7 days prior to the index date. Diagnostic codes for patients with “other indication” will be compiled for descriptive purposes only.

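### Indication for iron is recorded for every patient and acknowledged as a possible source of confounding, but neither the propensity score nor the secondary regression includes it

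*Protocol*

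**What the plan says.** - **Indication is measured.** Protocol II.G.4: "We will identify one or more indications for the use of parenteral iron for each patient". Table 6 has 16 named diagnosis groups plus an other category, coded over the 183 days up to and including the index date. A patient may have several.
- **The propensity score is fixed elsewhere.** Protocol II.G.5.a fits the score at each site with one common logistic model, "using the probability of receiving iron dextran as the dependent variable and covariates in Table 5 as independent variables". Table 5 lists age, gender, 18 yes/no allergy, comorbidity and drug variables, year of new use and clinical setting. It contains no Table 6 group: no chronic kidney disease, pregnancy, malabsorption, inflammatory bowel disease, cancer or chemotherapy, and no bleeding diagnosis.
- **The secondary regression** (II.G.6.a) adjusts for the same confounders.
- **The threat is acknowledged.** Protocol II.H.2: "Confounding could be introduced if iron dextran and other iron products are prescribed for different reasons that are also predictive of the outcome of interest".
- **Indication ends up descriptive.** On analyses stratified by indication, II.H.2 says "we anticipate that it is unlikely we will have adequate power to perform these stratified analyses" and then "In this case, indication will be used to describe the population of study".

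**The concern.** The protocol describes a confounding mechanism, collects the variable that captures it, and then leaves that variable out of every adjusted analysis. II.G.5.a defends the propensity score as the way to handle many measured confounders when events are few, and indication is one of the measured variables.

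The protocol itself makes both links plausible:

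- **Product choice.** Dialysis patients are excluded (II.B) partly because their prescribing appears different, so the plan accepts that clinical group can shape which product is used. Non-dialysis kidney disease, oncology, obstetric and gastrointestinal patients stay in the cohort with no covariate naming the group.
- **Outcome.** Section I.A lists paclitaxel among drugs with boxed warnings arising from anaphylaxis reports. Events are counted on the index day and the day after, and the first criterion in Table 2 does not require a particular allergen. A reaction to another infusion in that window could therefore count.

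At stake are both primary estimates, matched and stratified. The planned balance checks would not reveal the problem if they cover only Table 5. The secondary regression would not reveal it either, because it shares the gap.

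**Working it through.** **1. The plan's own figures.** No stated figure is in dispute, but Table 7 sets the scale. Inputs (II.G.7): 40,015 iron dextran users, 60,714 users of other products, Fisher exact test at 0.05. Taking 0.025 in the upper tail, exact power reproduces all 12 rows within 0.6 points. For example, baseline 2.05 per 10,000 with RR 2.80 gives 80.7% against 81.3% printed, and 8.50 with RR 1.75 gives 81.3% against 81.4%. The detectable relative risks therefore run from 1.70 to 2.80, and the relative risk said to matter for policy is 4.

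**2. Do rare events limit the propensity model?** Its dependent variable is receipt of dextran, not anaphylaxis.
- Table 5 terms, with year as categories: 4 (age) + 1 (gender) + 18 (yes/no) + 13 (year) + 2 (setting) = 38.
- Adding the 16 Table 6 groups: 38 + 16 = 54.
- Pooled dextran users per term: 40,015 / 38 = 1,053 now; 40,015 / 54 = 741 after.

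The roughly 35 to 122 events implied by Table 7 (40,015 × dextran risk + 60,714 × baseline risk, first and last rows) do not enter this count. Scores are fitted by site and site sizes are not given, so small sites will be tighter than the pooled figure.

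**3. How large could the bias be?** The document gives neither the frequency of any indication by product nor its association with anaphylaxis, so the inputs are assumptions: prevalence 10-40% in each group, a 2-3 fold difference between groups, and an effect *m* on anaphylaxis risk of 2-3. For one binary indication, with no help from proxies,

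factor = [1 + p_dextran(m − 1)] / [1 + p_other(m − 1)].

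| p_dextran | p_other | m | Factor |
|---|---|---|---|
| 0.40 | 0.20 | 2 | 1.40/1.20 = 1.17 |
| 0.40 | 0.20 | 3 | 1.80/1.40 = 1.29 |
| 0.30 | 0.10 | 3 | 1.60/1.20 = 1.33 |
| 0.40 | 0.133 | 3 | 1.80/1.267 = 1.42 |
| 0.20 | 0.40 | 3 | 1.40/1.80 = 0.78 |
| 0.10 | 0.30 | 3 | 1.20/1.60 = 0.75 |
| 0.133 | 0.40 | 3 | 1.267/1.80 = 0.70 |

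The extremes are 0.70 and 1.42. A true RR of 2.8 would read 2.8 × 0.70 = 2.0 to 2.8 × 1.42 = 4.0. A true RR of 4 could read as low as 4 × 0.70 = 2.8.

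**4. Effect on false positives.** With a true RR of 1, the full group sizes and the two-sided Fisher test by point probabilities:

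| Bias factor | Baseline 2.05 per 10,000 | Baseline 8.5 per 10,000 |
|---|---|---|
| 1.00 | 3.8% | 4.3% |
| 1.17 | 5.6% | 10.7% |
| 1.25 | 7.2% | 17.8% |
| 1.43 (just past the top of the range) | 12.9% | 41.4% |

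**The case against.** The strongest reply is that the score already contains much of what indication would add. Immunosuppressive therapy includes agents relevant to bowel disease (infliximab, adalimumab, azathioprine) and to oncology (cyclophosphamide, rituximab). Age and gender partly capture obstetric and menorrhagia use. Hypertension and ACE inhibitor or ARB use partly track kidney disease. Setting and year are included, matching is within site, and dialysis patients are excluded. The other mechanism in II.H.2, providers avoiding dextran in patients thought prone to anaphylaxis, is addressed directly by the allergy covariates. All of this stands, so residual bias may be smaller than the illustration. It remains adjustment by proxy: the immunosuppressive list, for example, names no taxane.

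Table 6 also lists potential indications, not confirmed reasons for treatment. That is fair, but a noisy measure of the confounder is still a usable covariate.

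Section I.F disclaims definitive causal evidence, and II.G.6.a allows Rosenbaum bounds if necessary. Those bounds address unmeasured confounding, whereas indication is measured.

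A reader might infer four stronger things that the document does not support:
- *That indication is called the main threat.* II.H.2 mentions it first but ranks nothing.
- *That a wrong reason is given for leaving it out of the score.* Low power is cited only against stratified analyses; the omission from the score is unexplained.
- *That confounding by indication is wholly unadjusted.* The proxies above contradict this.
- *That the primary estimates are shown to be biased.* That would need indication to predict both product and anaphylaxis given Table 5, and the document has no data on either.

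**Conclusion.** The point holds: a measured variable, tied by the protocol itself to confounding, is absent from both the propensity score and the secondary regression, with no stated reason. The covariate set is fixed here as Table 5, so this is not a detail left to a later plan.

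The supported conclusion is that confounding by indication is not directly adjusted and that both primary estimates could be biased, in an unknown direction. The range of 0.70 to 1.42 rests wholly on the assumed inputs, concerns one indication, and ignores the proxies. Several indications could add to one another or offset. A bias of that size matters against detectable relative risks of 1.70 to 2.80. It would not, on its own, carry a true RR of 1 to the policy value of 4, though it could move a true 2.8 close to it. This is best treated as a cheap improvement to make before the sites run their models, not as a demonstrated failure of the primary analysis.

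**What to change.** - Add the Table 6 indication flags as yes/no covariates to Table 5 and to the common site-level propensity model in II.G.5.a, with the rare cancer-site rows merged into one flag. The secondary regression then inherits them.
- Report standardized differences for these flags before and after matching and stratification.
- State in II.H.2 that low power rules out outcome estimates by indication, which remain descriptive, and that indication is adjusted for through the score.

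**Cost.** One sentence in II.G.5.a, some rows in Table 5 and up to 16 model terms, all from data already collected. Some flags will need merging at small sites, and slightly fewer patients may match.

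**Timing.** Sites send only counts of users and events by treatment group, or by treatment group within score strata. The project team could not add indication centrally afterwards, and each site would have to refit and resend. The change should be made before the models are run.
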